3. ABSTRACT

Prospective, multicentre, observational study in patients with metastatic renal cell carcinoma (mRCC) receiving a tyrosine kinase inhibitor as first-line treatment according to routine clinical practice, designed to evaluate the incidence of fatigue and hand-foot syndrome in order to determine how these affect the baseline characteristics of the patient and his/her disease (age, gender, baseline status, tumour histology, etc.) and the patient's lifestyle as such side effects develop.

[figure not shown]
STUDY TITLE

Prospective, multicentre, observational study on fatigue- and hand-foot syndrome-related quality of life in patients with metastatic renal cell carcinoma receiving a tyrosine kinase inhibitor as first-line treatment (TROYA Study)

PROTOCOL CODE: A6181218 (PFI-ITK-2015-01) TROYA

COORDINATING INVESTIGATOR:

The scientific coordinator will be responsible for maintaining the methodological rigour of the study, both in the design phase and in the evaluation of results and writing of the final report. He will guarantee the ethical conduct of the study, maintaining scientific support for all participating doctors until the results are published.

STUDY SITES:

It is initially considered optimal to include patients at approximately 35 Spanish sites (see ANNEX 7 to the protocol, which contains the list of proposed sites).

IEC THAT WILL ASSESS THE STUDY

IEC of Navarre

Secretary of the Independent Ethics Committee of Navarre (IEC) [name]

[contact] [contact] Email: [contact]

STUDY OBJECTIVES

PRIMARY OBJECTIVE

Fatigue-related quality of life of patients receiving a tyrosine kinase inhibitor evaluated using the validated 13-item FACIT-Fatigue scale for patients with metastatic renal cancer in Spanish.^{1,2}

SECONDARY OBJECTIVES

- 1) Quality of life in patients with palmar-plantar erythrodysaesthesia (hand-foot syndrome).
- 2) To assess the following adverse effects according to version 4 of the CTCAE (Common Terminology Criteria for Adverse Events): any grade of fatigue and hand-foot syndrome (HFS).
- 3) To study what role aerobic exercise (walking quickly, running, swimming, playing tennis, dancing and/or riding a bike) plays in the onset of fatigue before starting and during treatment.

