It is not clear what percentage of fatigue is cancer-related and what percentage is attributable to the tyrosine kinase inhibitor as both types of fatigue are very similar and often coexist. The mechanisms of fatigue are not well described. Changes at muscle level can cause peripheral fatigue, whereas central nervous system failure to activate the motor neurons adequately would cause central fatigue.

Fatigue is more common in men, particularly in young men, resulting in repeated treatment interruptions. However, fatigue tends to decrease with increasing treatment cycles. Whether this phenomenon represents an adaptation and/or learning by the patient or a true lower incidence is unknown.

It is important to rule out other causes that may cause or exacerbate fatigue, such as dehydration, hypothyroidism, hypercalcaemia, anaemia or depression. These adverse effects must be monitored every 2-3 cycles.¹³

In the phase I study published by Faivre,¹⁷ asthenia was associated with an increase in daytime napping and night-time somnolence. Age and baseline status (ECOG) at the start of the study did not predict asthenia.

Patient education is crucial. It is necessary to explain that this adverse effect will quite probably appear and we have strategies to manage it if it occurs.

It is interesting to see fatigue in the context of the disease and to readjust the patient's expectations, explaining that it will be necessary to adapt his/her everyday activities to save energy.¹³

Some authors recommend training with aerobic exercises for 30 minutes 3 times a week. Randomised clinical trials have demonstrated better responses in oncology patients using resistance training. It is important to take into account the patients' previous level of activity and cardiac output before recommending exercise.

RATIONALE FOR THIS STUDY

In view of the above, we believe it is appropriate to initiate a study to prospectively assess fatigue-related quality of life in patients with mRCC who are starting treatment with a tyrosine kinase inhibitor.

The patients' quality of life will be evaluated using the FACIT-Fatigue questionnaire and a Patient Diary (both to be completed by the patient) every 6 weeks.

To our knowledge, no fatigue-related quality of life studies in European patients with this condition have been published to date.

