#### 2.1 STUDY DESIGN

Prospective, multicentre, observational, post-authorisation study in patients aged  $\geq 18$  years diagnosed with metastatic renal cell carcinoma who are to be given a tyrosine kinase inhibitor as first-line treatment.

The study will evaluate measures to improve patients' quality of life, such as time of drug administration, napping, temporary treatment breaks and dose reductions.

Fatigue-related quality of life will be evaluated using the *Spanish version of the FACIT– Fatigue Questionnaire (see ANNEX 1)* which will be completed by the patient individually after it has been explained to them by the clinician or a person appointed by the investigator (nursing staff, clinical trials coordinator) in the treatment room during the scheduled visits, once the patient understands how to complete the form.

The FACIT–Fatigue questionnaire will be handed out at the following treatment times, which coincide with the visits, according to the site's protocol:

- 1) **Baseline** (before starting the treatment)
- 2) Month 3
- 3) Month 6
- 4) Month 9 or upon treatment discontinuation
- 5) Additional visits according to the oncology department's clinical practice: additional visits may be recorded on the case report form

The patient will also complete this FACIT-Fatigue questionnaire at home **at the start of each cycle** (for sorafenib and pazopanib a cycle will be 6 weeks of treatment), even if this does not coincide with scheduled visits to the hospital.

The hand-foot syndrome-related quality of life evaluation that patients may be asked to take part in will be performed on the basis of the CTCAE V4.03 2010 with scores running from 1 to 3 (see ANNEX 2).

The study will start at each site after the contract has been signed by all parties and all documentation and information on the procedures and objectives of the study have been received by the person appointed by the sponsor. Recruitment will be competitive between all the participating sites (estimating between 1 and 4 patients per site) and will finish once 100 patients have been recruited.

The investigator will be guided by routine clinical practice at all times when making decisions regarding the best available treatment option for the patient.

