#### TREATMENT

- 1) Time when the oral treatment is taken
- 2) Tyrosine kinase inhibitor dose and treatment regimen
- 3) Number of dose changes per treatment cycle
- 4) Temporary treatment interruptions, number of interruptions per treatment cycle
- 5) Best response achieved with first-line treatment
- 6) Mean duration of treatment
- 7) Time to treatment failure
- 8) How long each patient stays on first-line treatment/no. of cycles received
- 9) Reason for discontinuing the first-line drug
- 10) Date of disease progression and/or death

Through the analysis of the collected variables the following aspects will be assessed:

- **Progression-Free Survival (PFS):** defined as the interval from the start of treatment to the date of the first documentation of objective tumour progression or death from any cause.

- **Objective Response Rate (ORR):** Defined as the proportion of subjects who achieve complete remission (CR) or partial response (PR). In addition, subjects with stable disease (SD) will also be evaluated to obtain clinical benefit along with subjects with tumour progression. Subjects will be evaluated according to RECIST 1.1.

- **Duration of response (DOR):** in patients with PR or CR, it will be defined as the interval from the date the response is documented to the first date that progressive disease is observed.

- **Safety:** The safety of the tyrosine kinase inhibitor will be evaluated describing the incidence and all grades in the event of fatigue and or hand-foot syndrome.

- **Fatigue-related quality of life of patients:** this will be measured based on the results obtained after completion of the FACIT-Fatigue questionnaire by the patient.

- **HFS-related quality of life of patients** in cases in which HFS is present with a score from 1 to 3 according to version 4 of the CTCAE (Common Terminology Criteria for Adverse Events).

- Date of disease progression and/or death.

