## 8.2.3 Follow-up analysis

The evolution of the following aspects will be presented for each one of the follow-up visits of the patients at which the variables listed below are recorded:

- Presence of palmar-plantar erythrodysesthesia: the absolute and relative frequency of patients who as of month 3 of treatment develop palmar-plantar erythrodysesthesia of any grade will be provided. In the sub-population of patients with hand-foot syndrome, the frequency distribution will be presented according to the degree of severity of these AE, according to CTCAE (Common Terminology Criteria form Adverse Event) version 4:
  - o Grade 1
  - o Grade 2

#### o Grade 3

For each one of the evolution visits (month 6 and month 9), a study will be performed to ascertain whether significant changes have occurred in the presence and the grade of the HFS with regard to the previous visit, defined as (improved, maintained or worsened). The Pearson chi-squared test will be used for this purpose (or Fisher's exact test for 2x2 tables or likelihood ratio test for mxn tables, if necessary).

- Presence of fatigue: the absolute and relative frequency of patients with the presence of fatigue of any degree since the baseline visit will be provided. In the sub-population of patients with fatigue, the frequency distribution will be presented according to the degree of severity, according to CTCAE (Common Terminology Criteria form Adverse Event) version 4:
  - o Grade 1
  - o Grade 2
  - o Grade 3
  - o Grade 4

For each one of the evolution visits (month 3, month 6 and month 9), a study will be performed to ascertain whether significant changes have occurred in the grade of fatigue with regard to the previous visit, defined as (improved, maintained or worsened). Significant associations will be sought between the habits of daytime rest, physical aerobic exercise, medication taken, dose and treatment schedule changes, dose interruptions and the number of days of treatment interruption depending on the evolution of the presence and degree of fatigue in the last twelve weeks. The Pearson Chi-squared test will be used for this purpose (or Fisher's exact test for 2x2 tables or likelihood ratio test for mxn tables, if necessary).

- Patient diary data (weekly): the distribution of patient frequencies will be presented according to the following habits:
  - Napping
    - Every day
    - Weekend and/or holidays
    - Sporadically, between 2 or 6 days
    - Has not taken a nap any day

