## • Has taken the medication:

- In the morning (between 7 am and 12 noon)
- In the afternoon (between 1 pm and 7 pm)
- At night (between 8 pm and 6 am)
- I have not taken any medication this week

For each one of the weekly habits described above, a summary calculation will be made (after three months) of each patient's habits in terms of daytime rest, physical exercise and taking their medication, taking the options marked with greater frequency in the last 12 weeks into account.

FACIT\_Fatigue: The main measures of centrality and dispersion measures will be calculated (mean, standard deviation, median, minimum, maximum, IR and 95%CI ) from the score obtained in the FACIT\_Fatigue quality of life scale, calculated as described in ANNEX 1. The absolute and relative frequency of patients with severe fatigue, being those with a score of less than 30 points on the FACIT\_Fatigue scale, will also be presented.

For each one of the evolution visits (week 6, week 12, week 18, week 24, week 30 and week 36), a study will be performed to ascertain whether significant changes have occurred in fatigue-related quality of life versus the previous evaluation, and defined as:

- **Improvement:** if there is an increase of more than 4 points in the FACIT\_Fatigue scale score versus the previous evaluation
- **Maintenance:** if the score on the quality of life scale does not vary by more than 4 points versus the previous evaluation
- **Worsening:** if the score obtained on the Facit\_Fatigue scale decreases by more than four points versus the previous evaluation.

Significant associations will be sought between the habits of daytime rest, the practice of physical aerobic exercise, medication taken, dose and treatment schedule changes, dose interruptions and the number of days of treatment

interruption depending on the evolution in the evaluation of the fatigue in the FACIT\_Fatigue over the last six weeks. The Pearson chi-squared test will be used for this purpose (or Fisher's exact test for 2x2 tables or likelihood ratio test for mxn tables, if necessary).

- Treatment: For each one of the treatment cycles received by patients during the 9-month follow-up, the following will be studied:
  - **Dose change:** the absolute and relative frequency of patients who have changed doses since the last cycle will be provided. In the sub-population of patients with dose changes in the last cycle, their frequency distribution will be presented according to:

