#### 9 LIST OF TABLES AND TABLE OF CONTENTS

Table/Graph number			Table/Graph title					
1.			Included and evaluable population					
2.			Descriptive analysis					
	.1		Demographic and disease information					
		.1	Age					
		.2	Time from diagnosis and from the advanced diagnosis of the disease					
		.3	Gender					
		.4	ECOG at time of diagnosis, Heng prognostic criteria and site of metastasis					
		.5	Histological type					
		.6	Smoking					
	.2		Dosage and treatment regimen of tyrosine kinase with which the patient begins treatment					
3.			Analysis of evolution					
	.1		Presence of palmar-plantar erythrodysesthesia of any grade (month 3, month 6, month 9)					
		.1	Association between medication intake habits and evolution of hand- foot syndrome (every three months)					
		.2	Association between dose changes and evolution of hand-foot syndrome (every three months)					
		.3	Association between dose, treatment regimen received and the evolution of hand-foot syndrome (every three months)					
		.4	Association between temporary treatment interruptions and evolution of hand-foot syndrome (every three months)					
	.2		Presence of fatigue of any grade (baseline, month 3, month 6, month 9)					
		.1	Association between daytime rest habit and fatigue evolution (every three months)					
		.2	Association between daytime physical exercise and fatigue evolution (every three months)					
		.3	Association between daytime medication-taking habits and fatigue evolution (every three months)					
		.4	Association between daytime dose changes and fatigue evolution (every three months)					
		.5	Association between doses, daytime treatment regimen and fatigue evolution (every three months)					

CT24-GSOP-SD-GL04 NI Study SAP Template; Template Version 1.0, Effective 31-Dec-2013 Page 23 of 29

PFIZER CONFIDENTIAL

	.6	Association between temporary daytime interruptions and fatigue evolution (every three months)
	3	Data from the patient diary
	.1	Daytime rest (weekly)
	.2	Physical exercise (weekly)
	.3	Has taken the medication (weekly)
•-	4	Quality of life (FACIT_Fatigue) (every six weeks)
	.1	Association between daytime habit and evolution on the Facit_Fatigue (every six weeks)
	.2	Association between daytime physical exercise and evolution on the Facit_Fatigue (every six weeks)
	.3	Association between daytime medication-taking habits and evolution on the Facit_Fatigue (every six weeks)

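### The SAP reports fatigue prevalence by visit from baseline on, and never defines treatment-emergent fatigue, although its safety objective is the incidence of fatigue

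*SAP*

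**What the plan says.** The protocol abstract (section 3) describes a study "designed to evaluate the incidence of fatigue and hand-foot syndrome". The safety entry in SAP section 6 reads: "The safety of the tyrosine kinase inhibitor will be evaluated describing the incidence and all grades in the event of fatigue". SAP 6.2 likewise bases TKI safety on all CTCAE grades where fatigue is present, with no condition on when it began.

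The analysis is in SAP 8.2.3:

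- For CTCAE fatigue, "the absolute and relative frequency of patients with the presence of fatigue of any degree since the baseline visit will be provided". The lead sentence of that section is "The evolution of the following aspects will be presented for each one of the follow-up visits", and Table 3.2 in SAP section 9 is titled "Presence of fatigue of any grade (baseline, month 3, month 6, month 9"). By SAP 2.1 the baseline visit falls "before starting the treatment".
- At months 3, 6 and 9 the change in fatigue grade from the previous visit is classed as improved, maintained or worsened. This classification is then related to napping, exercise, time of intake, dose changes and interruptions.
- Each visit is compared with the previous visit and with baseline by sign or McNemar tests.
- For FACIT-Fatigue, the output is "The absolute and relative frequency of patients with severe fatigue, being those with a score of less than 30 points", together with a 4-point change rule against the previous evaluation.

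Hand-foot syndrome is handled differently in the same section. It is counted in patients who develop it on treatment, and its table has no baseline column.

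**The concern.** Presence at a visit and incidence on treatment are different quantities when patients can be fatigued before the first dose, and here they can. ECOG up to 2 is allowed, and no entry criterion excludes fatigue; only untreated hypothyroidism and untreated severe anaemia, among its possible causes, are excluded. Protocol section 5 adds: "It is not clear what percentage of fatigue is cancer-related and what percentage is attributable to the tyrosine kinase inhibitor", and says the two often coexist. The baseline grade is the main information in this study that could help separate them.

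A fatigue frequency at month 3, 6 or 9 mixes persisting baseline fatigue with fatigue that arose or worsened on treatment. At stake are secondary objective 2 (CTCAE fatigue of any grade) and objective 3 (exercise and the onset of fatigue). If incidence is left undefined, its definition will be chosen after the data have been seen.

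**Working it through.** Neither document gives an incidence figure or a baseline prevalence, so there is no planned number to reproduce. The check is what the planned outputs can and cannot recover.

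**1. Individual grade paths.** Treatment-emergent here means a grade after the first dose above the baseline grade. The change classes follow SAP 8.2.3.

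| Grade at baseline, month 3, month 6 | Fatigue present at | Planned change class, months 3 and 6 | Treatment-emergent? |
|---|---|---|---|
| 0, 0, 0 | no visit | maintained, maintained | no |
| 2, 2, 2 | all three | maintained, maintained | no |
| 0, 2, 2 | months 3 and 6 | worsened, maintained | yes, new onset |
| 1, 3, 3 | all three | worsened, maintained | yes, maximum grade 3 |
| 2, 0, 1 | baseline and month 6 | improved, worsened | no |

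Rows 1 and 2 share a change class although only one patient could have an onset. Row 5 is worsened at month 6 while below the baseline grade. At month 3 the previous scheduled visit is baseline, so worsened does then mean above baseline, unless an additional visit intervenes. From month 6 it does not.

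**2. Prevalence by visit.** Let b be baseline prevalence, r the share of baseline cases resolved by the visit, i the onset among patients free of fatigue at baseline, and p the prevalence at the visit:

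p = b(1 − r) + (1 − b)i, so i = [p − b(1 − r)] / (1 − b).

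Assume b = 30%, r = 1/3 and i = 50%. Then p = 0.30 × 2/3 + 0.70 × 0.50 = 0.20 + 0.35 = 55%. The tables would show 30% and 55%, a net rise of 25 points. Onset was 35% of all patients and 50% of those at risk.

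Now work back from 30% and 55% alone:

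- r = 0: i = (0.55 − 0.30) / 0.70 = 35.7%.
- r = 1: i = 0.55 / 0.70 = 78.6%.

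The displayed prevalences do not fix the incidence. The same holds for FACIT below 30 at successive evaluations.

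**3. Paired tests.** McNemar's test compares patients with fatigue at the visit only against patients with fatigue at baseline only. Per 100 patients, these are 35 and 10 in the example, 25 and 0 if r = 0, and 55 and 30 if r = 1. The net change is 25 in all three. The SAP plans the test but does not commit to reporting the first cell, its denominator or the maximum grade after the first dose.

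**4. Cost in precision.** SAP 5.1 gives 100 patients and 5% discontinuation, so 95. Patients at risk of new onset number 95(1 − b): 85.5 for b = 10% and 57 for b = 40% (assumed range). At 50% onset the 95% half-width is 1.96 × √(0.25/n): 10.1 points for 95, 10.6 for 85.5 and 13.0 for 57.

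**The case against.** The strongest reply is that the plan does not ignore baseline. It shows baseline as its own time point, classifies change at each visit and tests every visit against baseline. A move from grade 1 to grade 3 appears as worsened. The McNemar table contains the new-onset cell for that visit. All of this stands. What remains missing is a commitment to report that cell, a summary over the whole treatment period, and a maximum grade relative to baseline.

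Protocol section 9 also defines an adverse event as happening to a patient who has received a drug, starts the safety reporting period at first dose for patients not already exposed, and requires a causality assessment. Fatigue before the first dose is then arguably outside the adverse event record, and the safety incidence in SAP 6 and 6.2 need not be the frequency in 8.2.3. That is fair, but the SAP lists no other fatigue table and does not carry the first-dose rule into 8.2.3.

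The primary objective is FACIT-Fatigue quality of life in a descriptive study, so CTCAE fatigue is a secondary matter. Objective 3 speaks of onset both before and during treatment, so confining it to patients free of fatigue at baseline could remove part of it. Both points stand and limit the remedy.

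A reader might infer something stronger: that one pooled count from baseline on will be reported as TKI toxicity. With 50% true onset, that count would read 0.20 + 0.80 × 0.50 = 60% at 20% baseline prevalence and 0.40 + 0.60 × 0.50 = 70% at 40%. The documents do not support this. The lead sentence of 8.2.3 and Table 3.2 point to separate visit frequencies with baseline displayed, and no text labels baseline fatigue as drug toxicity. Nor do the documents show that the 50–75% asthenia rate in the rationale excludes baseline fatigue, so no mismatch with that figure can be claimed.

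**Conclusion.** The concern holds as a gap in definition. Fatigue incidence is named as a safety measure, but the planned outputs are prevalence by visit, change from the previous visit and tests of net change. None commits the study to reporting how many patients had fatigue that was new, or worse than before the first dose, over the treatment period.

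The size cannot be stated, because it depends on baseline prevalence and on how much baseline fatigue resolves. The span of 36% to 79% shows only that the visit tables leave incidence undetermined; it rests on the assumed prevalences of 30% and 55%. The conclusion reads the phrase about the baseline visit in 8.2.3 as prevalence at each visit from baseline on, which is the natural reading beside Table 3.2.

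**What to change.** In SAP 8.2.3 and Table 3.2:

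- Define treatment-emergent fatigue as a CTCAE grade after the first dose higher than the baseline grade. Report it overall and by maximum grade.
- Report new onset among patients with no fatigue at baseline, stating that denominator.
- For FACIT-Fatigue, report new scores below 30 among patients at 30 or above at baseline.
- Keep the visit-by-visit frequencies, labelled prevalence.
- For objective 3, add an analysis of exercise and onset in patients without fatigue at baseline, alongside the planned associations and not in their place.

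This takes a few lines of SAP text and a flag derived from baseline data already collected. The one drawback is that the onset analyses use fewer patients than the full sample, with the modest loss of precision shown above.

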## 4 HYPOTHESIS TESTING

The statistical significance value is set to p<0.05 The SPSS statistical package, V19.0 or later will be used.

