#### 5 ANALYSIS POPULATION

#### 5.1 FULL ANALYSIS SET

Plans are to include 100 patients in the study to receive first-line treatment over the course of 18 months at 35 sites.

This is a descriptive study; therefore, a specific number of patients is not required to calculate the sample size.

In order to study the fatigue-related quality of life of patients who are taking a tyrosine kinase inhibitor, evaluated using the validated 13-item FACIT-Fatigue scale for patients with metastatic renal cancer on Spanish, the inclusion of 100 patients with metastatic renal carcinoma who are about to receive first-line treatment with a tyrosine kinase inhibitor and who meet the screening criteria of the study is proposed.

This sample size will allow us to estimate percentages of patients with fatigue (severe/non-severe) during follow-up, with a 95% level of significance and an estimated proportion of 10%, assuming a discontinuation rate of 5%.

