#### 8 STATISTICAL ANALYSIS AND METHODOLOGY

#### 8.1 STATISTICAL METHODS

The investigator will collect data from the enrolled patients in an electronic Case Report Form specially designed for this study.

The patient number we provide is a serial number devoid of any identifying value.

The information is stored in an Access database, which in turn is associated with a file, "WorkGroup", detailing the user code and permits of the investigator within the database. People not within this working group cannot access the database.

A Data Management Plan (DMP) will be developed and once approved by the person responsible for the study, the "Queries" will be programmed in the electronic case form so that when the investigator saves the data, it informs him/her of any doubts regarding the data.

All changes made by the investigators during the collection of data will be stored in a table specially designed for this purpose, indicating the user, date, modified field, the old value and the new value.

The fatigue-related quality of life of the patients and the quality of life of patients with palmar-plantar erythrodysaesthesia (hand-foot syndrome) will be studied using the mean, standard deviation and confidence intervals if they follow normal distribution, or the median, minimum, maximum and interquartile range if they do not follow Gaussian distribution. The Wilcoxon test will be used to analyse the inter-visit correlation for patients' quality of life.

The objective response rate according to RECIST version 1.1 will be studied using absolute and relative frequencies.

In order to study the impact of drug administration time, napping, temporary interruptions and dose reductions on fatigue and hand-foot syndrome control, independent samples will be compared using Pearson's chi-square test (or Fisher's exact test for 2x2 tables or likelihood ratio test for mxm tables, if necessary) in the case of qualitative variables and Student's t-test, one-way ANOVA test or non-parametric equivalents, such as the Mann-Whitney U test or Kruskal-Wallis H test in the case of quantitative variables.

The Kaplan-Meier survival estimate will be used to study both the PFS and TTF of patients. The log-rank test will be used to compare the survival distributions.

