    - Number of dose changes received
      - 1 change \_ New dose
        - Sunitinib 50 mg 4/2 regimen
        - Sunitinib 50 mg 2/1 regimen
        - Sunitinib 37.5 mg 4/2 regimen
        - Sunitinib 37.5 mg 2/1 regimen
        - Sunitinib 25 mg 4/2 regimen
        - Sunitinib 25 mg 2/1 regimen
        - Pazopanib 800 mg/24 hours continuous
        - Pazopanib 400 mg/24 hours continuous
        - Sorafenib 400 mg/24 hours continuous
        - Sorafenib 400 mg/12 hours continuous
      - 2 changes\_ New dose
        - Sunitinib 50 mg 4/2 regimen
        - Sunitinib 50 mg 2/1 regimen
        - Sunitinib 37.5 mg 4/2 regimen
        - Sunitinib 37.5 mg 2/1 regimen
        - Sunitinib 25 mg 4/2 regimen
        - Sunitinib 25 mg 2/1 regimen
        - Pazopanib 800 mg/24 hours continuous
        - Pazopanib 400 mg/24 hours continuous
        - Sorafenib 400 mg/24 hours continuous
        - Sorafenib 400 mg/12 hours continuous
  - **Treatment interruptions:** the absolute and relative frequency of patients who have interrupted the treatment since the last cycle will be given. In

the sub-population of patients with treatment interruptions, their frequency distribution will be presented according to:

- Number of treatment interruptions
  - 1
  - 2
  - 3
  - 4 •
  - 5 •
  - ...
- Total calculation of days of treatment interruption
  - <7 days
  - 7-14 days
  - >14 days

In order to study the evolution of patients in terms of the presence of AEs (HFS and fatigue), patient habits in terms of daytime rest, aerobic physical exercise and taking medication, paired data comparisons will be performed between each one of the visits with the results of the previous visit, as well as of each one of the visits with regard to the results presented at the baseline visit, using, for this purpose, the non-parametric sign tests for categorical variables or the McNemar test in the case of dichotomous variables. In order to ascertain whether there is a significant evolution in the score obtained on the FACIT Fatigue scale throughout the study, comparisons of paired data will be performed for each one of the assessments with regard to the baseline value and with regard to the

previous evaluation using the Student t-test for paired data or the non-parametric Wilcoxon test, as appropriate.

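### SAP 8.2.3 tests the number of days of treatment interruption, a count, with categorical tests only; this is not reconciled with SAP 8.1, and Kruskal-Wallis on days would use the data better

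*SAP*

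**What the plan says.** Secondary objective 4 asks what impact several factors, temporary treatment breaks among them, have on controlling fatigue and hand-foot syndrome. SAP 8.2.3 turns this into association tests against fatigue evolution, classed as improved, maintained or worsened. The exposures include "dose interruptions and the number of days of treatment interruption depending on the evolution of the presence and degree of fatigue". That paragraph concerns CTCAE fatigue over the last twelve weeks. A parallel paragraph does the same for FACIT-Fatigue over the last six weeks. Both name Pearson chi-squared, with Fisher for 2x2 tables or likelihood ratio for larger tables if necessary, and no other test.

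SAP 8.1, like Protocol 7.7, deals with the impact of interruptions on fatigue and hand-foot syndrome and splits by variable type. Qualitative variables get the chi-squared family; the alternative is "Student's t-test, one-way ANOVA test or non-parametric equivalents, such as the Mann-Whitney U test or Kruskal-Wallis H test in the case of quantitative variables".

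The only categories for days are in the treatment part of SAP 8.2.3, under "Total calculation of days of treatment interruption": <7, 7-14 and >14 days. That table is made for each treatment cycle, covers only patients with an interruption and has no 0-day band. The SAP table list (section 9) has association tables for interruptions but none that names days by band.

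SAP 4 adds: "The statistical significance value is set to p<0.05".

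**The concern.** Days of interruption is listed separately from interruption yes/no, so it is the exposure that carries the amount of interruption. Chi-squared, Fisher and likelihood ratio tests cannot take a count without cut-points, and in tables larger than 2x2 they treat <7, 7-14 and >14 as unordered labels. The plan therefore leaves two things open: which test family applies (8.1 or 8.2.3), and, if 8.2.3 is followed, which categories are used and where patients with no interruption go. Cut-points could then be chosen after the data are seen. If the descriptive bands are borrowed, the test discards both amount and order in a study of 100 patients of whom only a minority will have any days to count.

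**Working it through.** **1. The plan's own figures.** SAP 5.1 states "Plans are to include 100 patients in the study to receive first-line treatment over the course of 18 months at 35 sites", and bases this on "an estimated proportion of 10%, assuming a discontinuation rate of 5" per cent, without giving a precision. Back-solving n = z²p(1−p)/d² with p = 0.10 and d = 0.06: 1.96² × 0.09 / 0.0036 = 96.04, so 97; 97 / 0.95 = 102.1, so 103, close to 100. With d = 0.05 the result is 147, and with d = 0.07 it is 75. With 95 evaluable patients the half-width is 1.96 × √(0.09/95) = 0.060. This concerns estimating a proportion. No power, effect size or distribution of interruption days is given for objective 4, so there is no planned power to reproduce.

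**2. Degrees of freedom.** Three bands by three outcomes give (3−1)(3−1) = 4 df; adding a 0-day row gives (4−1)(3−1) = 6 df. Kruskal-Wallis across three groups has 2 df. At equal noncentrality and alpha 0.05, 80% power on 2 df becomes 70% on 4 df and about 62% on 6 df.

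**3. Sparse cells.** Take 95 evaluable patients. The background sections cite 38% with a temporary interruption in the sunitinib pivotal trial. Then 95 × 0.38 = 36 patients spread over 3 × 3 = 9 cells, a mean expected count of 4.0. If 20% interrupt within a window (assumed), 95 × 0.20 = 19 patients, or 2.1 per cell. In simulation of the four-row table, about 48-57% of expected counts were below 5 at 38% interrupted, and about 73% at 20%. The likelihood ratio fallback for larger tables then rejected in about 5-10% of runs with no effect, depending on the scenario, against about 5% for Kruskal-Wallis.

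**4. Power, FACIT-type outcome.** Assumptions, none of them from the documents except the 4-point cut and the 38%: n = 95; days among interrupters log-normal, median 10, log-SD 0.8, capped at 42; SD of FACIT change 9; effect 0.2, 0.3 or 0.4 points per day; change cut into three categories at more than 4 points; 1,000 replicates. Each cell shows chi-squared on bands (0, <7, 7-14, >14) against Kruskal-Wallis on days.

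| Interrupted in window | 0.2 per day | 0.3 per day | 0.4 per day |
|---|---|---|---|
| 38% | 13 vs 23% | 30 vs 41% | 48 vs 64% |
| 20% | 8 vs 12% | 15 vs 25% | 24 vs 36% |
| 10% | 4 vs 6% | 8 vs 14% | 10 vs 20% |
| 5% | 2 vs 6% | 2 vs 6% | 2 vs 10% |

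The chi-squared figures below 5% show that the test is conservative in very sparse tables.

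**5. Power, generic three-category outcome.** A second model makes no use of FACIT points. It sets a latent correlation rho between days and an outcome split 30/40/30, with median 8 days and log-SD 0.8. Chi-squared against Kruskal-Wallis:

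- Interrupters only, n = 38: rho 0.2, 10 vs 12%; rho 0.3, 17 vs 24%; rho 0.5, 48 vs 69%.
- Interrupters only, n = 95: rho 0.3, 43 vs 63%; rho 0.5, 94 vs 99%.
- All patients, 62% at 0 days, n = 95: rho 0.3, 31 vs 49%.

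Variants with a 15/70/15 split, or with group shifts of 0.5 to 0.8 SD at n = 30 to 95, stayed within the same range. Over all non-null scenarios the gain from Kruskal-Wallis ran from 2.2 to 21.5 points. With no effect, chi-squared and Kruskal-Wallis both rejected in about 4-6% of runs in this model.

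**6. Trend alternative.** A Spearman-type test gained about 6 to 34 points over chi-squared when the relation was monotone, but lost about 9 to 43 points when it was U-shaped.

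**The case against.** The strongest reply is that the plan never says days are banded for the test. That is correct. The bands sit in a per-cycle frequency table of interrupted patients, while the associations use six- and twelve-week windows. The 0-day row in the calculation was added for this check. A reader might infer that <7, 7-14 and >14 are the test categories; the documents do not establish it. This does not clear the plan, because without those bands a chi-squared test is prescribed on a count with no categories at all.

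A reader might also say that 8.2.3 contradicts 8.1. That goes too far. Once banded, days can count as qualitative and chi-squared complies with 8.1; left as a count, 8.1 already supplies Kruskal-Wallis. The defect is an unreconciled choice.

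Third, the 38% comes from a sunitinib trial, with no time window stated, so the share interrupting within six or twelve weeks may be well below it. At 20% or less, neither test exceeded 36% power in the table above, so the change would not make the question answerable. This stands. So does the point that the FACIT model does not represent change in CTCAE grade; only the generic model bears on that outcome, and only loosely.

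Lastly, SAP 5.1 says "This is a descriptive study; therefore, a specific number of patients is not required to calculate the sample size". The missing power target is therefore deliberate. But the SAP still looks for significant associations at p<0.05, so the choice of test matters.

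**Conclusion.** The concern holds in limited form. SAP 8.2.3 assigns a count to tests that need categories and ignore order, and does not reconcile this with SAP 8.1 and Protocol 7.7. If the descriptive bands are used with a 0-day row, chi-squared has less power than Kruskal-Wallis on days in every non-null scenario tried, by roughly 2 to 22 points. That range depends on the assumed scenarios (n about 30 to 95, 5-38% interrupted per window where all patients are included, and assumed effect sizes). It must not be read as a fixed loss, or as a loss of planned power, since the documents state none. Many expected counts would fall below 5, and the likelihood ratio fallback can exceed its 5% error rate. The consequence is confined to one exposure in an unpowered secondary objective, so this is a cheap improvement and does not threaten the primary result.

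**What to change.** In SAP 8.2.3, in both the CTCAE and the FACIT-Fatigue paragraphs, state that total days of treatment interruption in the relevant window (twelve or six weeks; 0 if none) are analysed as a quantitative variable and compared across improved, maintained and worsened by Kruskal-Wallis, in line with SAP 8.1. State that the <7, 7-14 and >14 day bands are for description only. Spearman correlation of days with FACIT change may be added as supportive, with a note that it assumes a monotone relation; that may fail here, since patients may interrupt because of fatigue.

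The cost is SAP wording. No new data are needed, provided interruption days can be summed over the windows as well as by cycle. The downside is that a rank comparison is harder to display than a banded table, which can still be printed beside it.
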